## 10 Statistical Analysis Plan

---

### 10.1 Sample size

---

Based on historical data, a sample size of 14 completing subjects is sufficient to detect a non-inferiority margin of 0.1 logMAR for the primary variable, visual acuity, assuming  $\alpha=0.05$  and a power of 80% (Table 3).

Table 3: Primary variable (acuity) sample size calculation

Non-inferiority margin for logMAR visual acuity	Mean individual standard deviation	Sample size, Power 80% ( $p = 0.05$ )
-0.1	0.07	14

Based on historical data, a sample size of 53 completing subjects is sufficient to detect a non-inferiority margin of -0.75 for the secondary variable, comfort, assuming  $\alpha=0.05$  and a power of 80% (Table 4).

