*Subjects will be asked to wear lenses for **at least 3 hours** prior to the visit appointment.*

- Subjective responses will be collected per the Final Questionnaire [REDACTED] including:
  - Overall satisfaction (7-point Likert scale)
  - Comfort satisfaction & comfort rating (7-point Likert & 100-point scales)
  - [REDACTED]
  - [REDACTED]
  - [REDACTED]
  - [REDACTED]
  - [REDACTED]
  - [REDACTED]
  - [REDACTED]

- [REDACTED]
  - Lens handling (7-point Likert & 100-point scales)
  - [REDACTED]
  - [REDACTED]
  - Lens holding/handling (5-point Likert scales)
  - Vision (7-point Likert & 100-point scales)
- The following information will be collected from the subject by the investigator:
    - Wear time at visit (hours).
    - Average time of insertion and removal during previous week, i.e. average time (hours).
    - Maximum wear time during previous week (hours).
    - Average time of day lenses become uncomfortable, if at all, i.e. average comfortable wear time (hours).
    - Use and frequency of comfort / re-wetting drops during past week (if any).
  - Monocular and binocular **HIHC** and **HILC** distance logMAR visual acuities will be recorded (a spherical over-refraction will be performed for the distance eye and recorded first if the subject is wearing monovision).
  - Lens surface will then be assessed and graded per guidelines detailed in the CVI grading scales [REDACTED]
    - [REDACTED]
    - Wettability (0-4 scale)
    - [REDACTED]
    - [REDACTED]
  - Lens fit will then be assessed and graded according to the guidelines detailed in CVI Grading scales [REDACTED]
    - Lens centration (0.1mm steps)
    - [REDACTED]
    - Post-blink movement (0.1mm steps)
    - Mobility rating (0.50 steps)
    - Overall lens movement (-2 to +2 scale)
    - Overall lens fit acceptance and investigator reason, if unacceptable (0.25 steps). Video will be recorded in the event of poor fit.
  - The lenses will be removed and stored in either an unbuffered or phosphate buffered (not borate) saline for return to the Sponsor.

- Slit lamp biomicroscopy will be assessed according to the CVI approved study biomicroscopy CRF [REDACTED]

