**Table 2: Summary of Visits and Procedures**

	Visit 1a Screening / Baseline	Visit 1b Dispense Pair 1	Visit 2 2-week follow-up Pair 1 & Dispensing of Pair 2	Visit 3 2-week follow- up Pair 2 & Exit
Informed consent	✓	-	-	-
Meet inclusion/exclusion criteria	✓	-	-	-
History at baseline	✓	-	-	-
Demographics	✓	-	-	-
Wearing time	✓	-	✓	✓
HVID / palpebral aperture size	-	✓	-	-
Auto-refraction & keratometry	✓	-	-	-
Sphero-cylindrical refraction	✓	-	-	-
HIHC & HILC VAs with sphero-cylindrical refraction	✓	-	-	-
Slit lamp biomicroscopy	✓	✓*	✓	✓
Instillation of lens at office	-	✓	✓	-
Subjective assessments	-	✓	✓	✓
Lens surface assessments	-	✓	✓	✓
Lens fit assessments	-	✓	✓	✓
Spherical over-refraction (SOR)	-	✓	✓	-
HIHC & HILC Distance VAs (with CLs)	-	✓	✓	✓
Lens Preference Questionnaire	-	-	-	✓
Exit VAs	-	-	-	✓
Study Exit	-	-	-	✓

\* Not applicable if Visit 1b occurs on the same day as Visit 1a

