**Table 4: Secondary variable (comfort) sample size calculation**

Non-inferiority margin for comfort	Mean individual standard deviation	Sample size, Power 80% (p = 0.05)
-0.75	1.3	53

Consequently, a sample size of approximately 60 completing subjects is sufficient for this study.

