## 10.2 Statistical analysis

---

Summary statistics will be produced (e.g. mean, standard deviation). Paired t-test will be used to compare slit lamp biomicroscopy, lens fit and subjective scores between study lens types. Repeated Measures Analysis of Variance (ANOVA) or paired analysis will be used to compare the variables between study visits. The critical alpha level for statistical significance will be set at  $p \leq 0.05$ , with adjustment for multiple comparisons.

All participants who were evaluated will be used in the analysis. In the event of missing data, individual data points will be excluded in the analysis and not extrapolated from the collected data.

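### Section 10.1 sizes acuity and comfort for non-inferiority, but 10.2 tests neither against its margin, and 14 and 53 do not both follow from one paired calculation with the printed inputs

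*Combined protocol and SAP*

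**What the plan says.** **Sizing (section 10.1, Tables 3 and 4).** For acuity, "a sample size of 14 completing subjects is sufficient" at a margin of 0.1 logMAR (printed as -0.1 in Table 3) and an SD of 0.07. For comfort, "a sample size of 53 completing subjects is sufficient to detect a non-inferiority margin of -0.75 for the secondary variable, comfort", with an SD of 1.3. Both rows cite historical data, alpha 0.05 and 80% power, and both call the SD "Mean individual standard deviation". The section ends: "Consequently, a sample size of approximately 60 completing subjects is sufficient for this study". It does not say whether the SD is within-subject or of paired differences, whether alpha is one- or two-sided, or what true difference was assumed.

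**Analysis (section 10.2).** "Paired t-test will be used to compare slit lamp biomicroscopy, lens fit and subjective scores between study lens types". Repeated-measures ANOVA or a paired analysis compares variables between visits. Significance is at 0.05, "with adjustment for multiple comparisons". No margin, confidence limit or non-inferiority test appears, and no adjustment method or family is given.

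**Measures.** Table 2 lists "HIHC & HILC Distance VAs (with CLs" at Visits 1b, 2 and 3, and section 7.3 has these taken monocularly and binocularly. Comfort is collected at both two-week visits as "Comfort satisfaction & comfort rating (7-point Likert & 100-point scales". Neither sizing table says which measure its margin and SD belong to.

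**The concern.** The sample size and the analysis answer different questions. Section 10.1 asks whether the Test lens is worse than Control by less than a stated amount. Section 10.2 asks whether a difference can be detected, and the hypotheses in section 2.1 are worded as absence of difference. If a non-significant result is read as support for those hypotheses, imprecise data help the sponsor. So does the multiplicity adjustment, because it makes a difference harder to declare.

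The between-lens test does not list logMAR acuity, the variable that section 10.1 calls primary. Questionnaire ratings of vision would count as subjective scores; measured acuity would not.

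The two sizes are described identically and differ only in margin and SD, so a reader would expect one formula to give both. Comfort sets the study size, so its basis should be traceable.

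**Working it through.** **Inputs.** Margins 0.1 and 0.75, SDs 0.07 and 1.3, alpha 0.05, power 80% (section 10.1 and Tables 3 and 4); 60 completers (sections 7.1 and 10.1); paired data (crossover, section 3). True difference is not stated; I take 0, in line with section 2.1. SD type and sidedness are not stated, so I run both readings of each.

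**Formula.** Normal approximation: n = (SDd/M)² × (z(1-a) + z(0.80))², where SDd is the SD of the paired difference and M the margin. SDd is the printed SD, or the printed SD × √2 if that is within-subject. The exact version takes the smallest n at which the noncentral t, with n-1 degrees of freedom and noncentrality M√n/SDd, gives at least 80% power.

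**Step 1: reproduce 14 and 53.** (0.07/0.1)² = 0.49 and (1.3/0.75)² = 3.004. The z factor is 6.18 at one-sided 0.05 and 7.85 at one-sided 0.025.

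| Reading of SD | One-sided a | Acuity: approx., exact n | Comfort: approx., exact n |
|---|---|---|---|
| Paired difference | 0.05 | 3.03, **5** | 18.6, **20** |
| Paired difference | 0.025 | 3.85, **7** | 23.6, **26** |
| Within-subject (× √2) | 0.05 | 6.06, **8** | 37.2, **39** |
| Within-subject (× √2) | 0.025 | 7.69, **10** | 47.2, **50** |

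No row gives 14 and 53. A shared formula implies a ratio near 3.004/0.49 = 6.1 before rounding and the t correction; the printed ratio is 53/14 = 3.8. Putting any common multiplier on both SDs does not help: comfort 53 forces acuity 10 (0.05) or 11 (0.025), and acuity 14 forces comfort 70 or more.

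**Step 2: each figure alone.**
- *53.* At one-sided 0.025 and 80% power with SD × √2, n is 53 for SDs of about 1.34 to 1.349, which print as 1.3. Acuity is then 10 at SD 0.07, and 11 even at 0.0749.
- *14.* It is not reproduced by a paired calculation at 80% power and zero difference, even at the rounding limits of the SD. A two-sample formula gives 7 per arm, total 14 (one-sided 0.05), but comfort is then 76 in total.
- *Unstated true deficits.* With SD × √2, deficits of 0.028-0.0305 logMAR and 0.1075-0.1125 comfort points give 14 and 53 at one-sided 0.05. At 0.025 they are 0.0165-0.0195 and 0.0225-0.0275.

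**Step 3: power at 60 completers, unadjusted, true difference 0.** Comfort: 99.7% (0.05) or 99.3% (0.025) if 1.3 is the SD of differences; 93.0% or 87.5% if within-subject. Acuity: above 99.9% on every reading.

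**Step 4: if the adjustment reaches comfort.** The Bonferroni method and the number of splits are my assumptions. With 1.3 as within-subject:

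| Splits | From one-sided 0.05 | From one-sided 0.025 |
|---|---|---|
| 2 | 87.5% | 80.3% |
| 3 | 83.4% | 75.5% |
| 4 | 80.3% | 71.9% |
| 5 | 77.7% | 69.0% |

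If 1.3 is the SD of differences, power at five splits is still 97.9% or 96.1%.

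**Step 5: why a test of difference does not do the job.** Take n = 60, the √2 reading, a 95% interval (t = 2.001 on 59 df) and hypothetical observed differences, Test minus Control.
- Comfort: half-width 2.001 × 1.3 × √2/√60 = 0.475. An observed -0.40 is not significant, yet its lower limit is -0.875, beyond -0.75.
- Acuity: half-width 2.001 × 0.07 × √2/√60 = 0.026. An observed +0.03 is significant, yet its upper limit is 0.056, well inside 0.1.

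The two tests can disagree in both directions.

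**The case against.** Nothing in section 10.1 says the two rows share a formula, an SD type or a true difference. They are separate tables resting on historical data that the reader cannot see. The figure that sets the study size can be reached on the plan's own terms once rounding of the SD is allowed, and 14 affects nothing because acuity has ample power at 60. Section 2 calls this a feasibility study, so a strict testing hierarchy may seem more than it needs. Parts of the questionnaires are redacted or not shown, and they may identify the comfort scale.

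Most of this stands. It makes the sizing problem one of unstated inputs rather than of too few subjects. A reader might infer from the exact match of 53 with two other designs (equivalence at 0.05 with 80% power, or non-inferiority at one-sided 0.05 with 90%, both with SD × √2) that comfort was really sized for one of them. The documents do not support that: text and table both say non-inferiority and 80%.

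The objection does not reach section 10.2, which carries no redaction marks. One might say acuity falls under the between-visit comparison, but that too is described without a margin. Feasibility status does not remove the mismatch, since the plan itself chose margins, alpha and power.

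**Conclusion.** The point holds. Followed as written, section 10.2 cannot support the non-inferiority conclusions for which section 10.1 sizes the study, and it leaves the between-lens analysis of the primary variable unnamed. Separately, 14 and 53 are not jointly reproducible from the printed inputs with zero true difference; 14 needs an unstated deficit or another method.

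Two stronger readings should be resisted. One is that 60 completers is too few: both printed sizes exceed every paired 80% result at the printed SDs. The other is that the multiplicity clause leaves comfort underpowered. That requires the adjustment to cover comfort, 1.3 to be a within-subject SD, and an assumed Bonferroni split of at least 3 (from one-sided 0.025) or 5 (from 0.05). The documents settle none of these, and the clause follows the between-visit sentence, so its reach is unclear. What can be said is that method and family are missing and that section 10.1 makes no allowance for them.

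This should be corrected before analysis. It is not a reason to change the number of subjects.

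**What to change.** Keep 60 completers.

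1. **Section 10.2.** Conclude non-inferiority in acuity if the upper paired confidence limit of Test minus Control is below +0.1 logMAR (higher logMAR is worse, so this also settles the sign in Table 3). Only if that is met, and at the same full alpha, conclude non-inferiority in comfort if the lower limit of Test minus Control is above -0.75. State the confidence level. Name one acuity measure and visit (for example, binocular HIHC at the two-week visit) and the one comfort scale to which 0.75 and 1.3 belong. Apply a named adjustment, such as Holm, only to the remaining variables, or report them descriptively.
2. **Tables 3 and 4.** Recompute each row with SD type, sidedness and assumed true difference stated, and restate power at 60. The rows need not share a true difference.

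Because acuity power at 60 is above 99.9%, testing it first costs comfort essentially nothing: with zero true differences, power to pass both is about 93% (one-sided 0.05) or 87% (0.025) on the √2 reading.

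The cost is two restated table rows and a few sentences, with no added subjects, visits or measurements. The downside is weaker or no formal claims for variables after comfort, and no formal comfort claim if acuity fails.

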**Table 4: Secondary variable (comfort) sample size calculation**

Non-inferiority margin for comfort	Mean individual standard deviation	Sample size, Power 80% (p = 0.05)
-0.75	1.3	53

Consequently, a sample size of approximately 60 completing subjects is sufficient for this study.

## 10.2 Statistical analysis

---

Summary statistics will be produced (e.g. mean, standard deviation). Paired t-test will be used to compare slit lamp biomicroscopy, lens fit and subjective scores between study lens types. Repeated Measures Analysis of Variance (ANOVA) or paired analysis will be used to compare the variables between study visits. The critical alpha level for statistical significance will be set at  $p \leq 0.05$ , with adjustment for multiple comparisons.

All participants who were evaluated will be used in the analysis. In the event of missing data, individual data points will be excluded in the analysis and not extrapolated from the collected data.

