## 2 Study Objective

---

This is a feasibility study to evaluate the clinical performance of a new silicone hydrogel formulation lens (Orion) in comparison with Gemini A ██████ over a period of two weeks of wear.

The primary variables of interest are:

- Vision

The secondary variables of interest are:

- Comfort/comfort preference
- Surface wettability performance
- Lens fit
- Lens handling
- Anterior ocular health

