### 2.1 Study Hypothesis

---

The primary hypothesis is that there will be no difference in vision performance between the Orion Test lens and the Gemini Control lens.

The secondary hypothesis is that there will be no difference in performance between the Orion Test lens and the Gemini Control lens for any of the secondary variables.

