### **3.1 Study Design & Comparator Justification**

---

The study design was chosen since the influence of confounding covariates is reduced in crossover designs, as each subject acts as his or her own control. Crossover study designs are also statistically more efficient.

The choice of comparator was made since the aim of the project is to match the clinical performance of the Gemini (Acquiane) lens, which is CE-marked / already approved in Europe.

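### The trial is sized on non-inferiority margins, but the analysis section has no rule that uses them and its between-lens test does not name logMAR acuity, the primary variable

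*Combined protocol and SAP*

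**What the plan says.** Section 10.1 frames both sample-size calculations as non-inferiority. For acuity, "a sample size of 14 completing subjects is sufficient to detect a non-inferiority margin of 0.1 logMAR for the primary variable, visual acuity"; Table 3 gives an SD of 0.07 and prints the margin as -0.1. For comfort, 53 completers "is sufficient to detect a non-inferiority margin of -0.75 for the secondary variable, comfort"; Table 4 gives an SD of 1.3. Both use 80% power and alpha 0.05, with no statement of one- or two-sidedness. The section ends: "Consequently, a sample size of approximately 60 completing subjects is sufficient for this study".

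Section 10.2 does not mention non-inferiority, a margin or a confidence interval, and nothing in it is blacked out. Its between-lens sentence is "Paired t-test will be used to compare slit lamp biomicroscopy, lens fit and subjective scores between study lens types". The next sentence applies repeated-measures ANOVA or a paired analysis to unspecified variables, compared across visits. Significance is set at p ≤ 0.05 with an adjustment for multiple comparisons that is not described.

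Section 2.1 carries no margin either: "The primary hypothesis is that there will be no difference in vision performance between the Orion Test lens and the Gemini Control lens". Section 3.1 explains the comparator by saying "the aim of the project is to match the clinical performance of the Gemini" lens. Section 2 sets the context: "This is a feasibility study to evaluate the clinical performance of a new silicone hydrogel formulation lens".

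**The concern.** A non-inferiority trial is decided by where the confidence limit for the Test-minus-Control difference falls relative to the margin. A difference test asks whether that difference is zero. A significant result does not show that Test is unacceptably worse, and a non-significant one does not show that it is acceptably close. Sections 2.1 and 10.2 both speak of difference, so the odd one out is Section 10.1, which alone determines the trial's size.

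The primary variable has a second problem: no sentence clearly gives it a between-lens test. Subjective vision ratings fall under subjective scores, but Section 10.1 defines the primary variable in logMAR. Acuity is also recorded in several forms. Under Visit 2 (Section 7.3.3), monocular and binocular, high- and low-contrast "distance logMAR visual acuities will be recorded (a spherical over-refraction will be performed" first for monovision wearers), and the same set is taken at dispensing. With no measure or time point named, the primary result could be chosen after the data are seen.

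At stake is whether the report's main statement follows from the evidence: a trivial acuity gap could be reported as a difference between lenses, or a comfort shortfall reported as none.

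**Working it through.** **1. Inputs.** From the documents: margins 0.1 logMAR and 0.75; SDs 0.07 and 1.3; about 60 completers; paired crossover. The tables label the SD only as a mean individual SD, so the SD of paired differences, s, is an assumption: either the tabled value or √2 times it. That gives 0.07 or 0.099 for acuity and 1.3 or 1.84 for comfort. Results below are in that order. Also assumed: true acuity gaps of 0.01 to 0.03 logMAR, and adjusted alphas of 0.01 and 0.0025.

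**2. The plan's own figures.** No single method tried gives both 14 and 53.
- Paired one-sided non-inferiority at 80% power needs 5 or 8 for acuity and 20 or 39 for comfort at one-sided 0.05; at one-sided 0.025 it needs 7 or 10, and 26 or 50.
- The stated numbers exceed all of these, so the trial is not shown to be underpowered.
- The figure 53 appears with s = 1.84 either as two one-sided equivalence tests at 80% power or as one-sided non-inferiority at 90% power, so it does not reveal which claim was intended.

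**3. Cut-offs at n = 60.** The standard error is s/√60: 0.00904 or 0.01278 for acuity, 0.168 or 0.237 for comfort. With 59 df the critical t is 2.001 (two-sided 0.05), 2.662 (0.01), 3.159 (0.0025) and 1.671 (90% interval).
- Smallest significant difference = t × SE. Acuity at 0.05: 2.001 × 0.00904 = 0.018, or 2.001 × 0.01278 = 0.026.
- Largest observed loss that meets the margin by a 90% interval = margin − 1.671 × SE. Acuity: 0.100 − 0.015 = 0.085, or 0.100 − 0.021 = 0.079. Comfort: 0.750 − 0.280 = 0.470, or 0.750 − 0.397 = 0.353.

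An observed acuity loss between 0.018 and 0.085 (or 0.026 and 0.079) is therefore both significant and non-inferior. The lower ends rise to 0.024 or 0.034 at alpha 0.01, and to 0.029 or 0.040 at 0.0025.

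**4. Acuity: chance of a significant difference** (noncentral t, 59 df, noncentrality gap × √60 / s):

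| True gap (logMAR) | alpha 0.05 | alpha 0.01 | alpha 0.0025 |
|---|---|---|---|
| 0.01 | 19% or 12% | 7% or 4% | 3% or 1% |
| 0.02 | 59% or 34% | 34% or 15% | 19% or 6% |
| 0.03 | 90% or 64% | 74% or 38% | 57% or 22% |

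Non-inferiority is met in at least 99.9% of trials in every cell. In the other direction, a true loss of 0.1 is non-significant with probability of at most 4 in a million.

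**5. Comfort: true deficit of 0.75.**

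| | alpha 0.05 | alpha 0.01 | alpha 0.0025 |
|---|---|---|---|
| Chance of a non-significant result | 0.7% or 12.5% | 3.9% or 31% | 10% or 49% |
| Smallest significant deficit | 0.336 or 0.475 | 0.447 or 0.632 | 0.530 or 0.750 |

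A one-sided 0.05 non-inferiority test would pass such a deficit 5% of the time. Observed deficits that are non-significant yet fail the margin by a 90% interval lie between the cut-off in step 3 and the threshold in this table:
- s = 1.3: none at 0.05 or 0.01; 0.47 to 0.53 at 0.0025.
- s = 1.84: 0.35 to 0.47 at 0.05; 0.35 to 0.63 at 0.01; 0.35 to 0.75 at 0.0025.

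**6. Does the between-visits sentence supply the acuity test?** In a randomised crossover, Visit 3 minus Visit 2 is Control minus Test in one sequence and Test minus Control in the other. Pooled by visit, the lens effect tends to cancel and a period effect remains. Read literally, it is not a lens comparison.

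**The case against.** The best defence is that this is loose wording in a feasibility protocol. The variables in the between-visits sentence may be the variables of interest in Section 2, which include vision, and a paired analysis is offered there. The promised means and SDs would let a reader set an acuity difference against the 0.1 margin unaided. Missing a margin-sized acuity loss is practically impossible. The comfort harm is conditional: with s = 1.3, the non-significance rates of 0.7% at 0.05 and 3.9% at 0.01 are below the 5% that a one-sided 0.05 non-inferiority test allows. The acuity gaps and adjusted alphas are not in the documents.

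Much of this stands as a limit on size. The comfort excess needs the larger SD, a strict adjusted alpha, or a 95% interval as the standard: with s = 1.3 and alpha 0.01, a 95% interval gives a conflict window of 0.414 to 0.447. The acuity risk is a wrong label, not a missed loss. None of it supplies the missing rule. Even if acuity is meant to be covered, the sentence compares visits, not lenses, and carries no margin. Feasibility status does not help much either, since the plan itself set margins, alpha and power.

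**Conclusion.** The concern holds and should be fixed. The mismatch between Sections 10.1 and 10.2 is a matter of text and depends on no assumption: margins set the sample size, no analysis rule uses them, and logMAR acuity is absent from the between-lens sentence. For comfort the planned paired t-test already yields the estimate and standard error, so only the decision rule is missing.

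The size depends on the undefined SD, the undefined multiplicity adjustment and the assumed true gaps. For acuity, a gap well inside the margin can readily be called a significant difference. For comfort, the chance that a margin-sized deficit is read as no difference runs from under 1% to about half across the assumed range. The consequence is an unclear or mislabelled conclusion, not an unsafe one.

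**What to change.** Edit Sections 2.1 and 10.2 before unmasking:

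- Name one logMAR acuity measure and time point, and one comfort item and scale (7-point and 100-point versions are both collected). Analyse each as a within-subject Test-minus-Control difference.
- Report the confidence interval: 90% if the alpha in Section 10.1 is one-sided 0.05, 95% if it is one-sided 0.025. State which.
- Conclude acuity non-inferiority if the upper limit is below +0.10 logMAR (higher is worse; reconcile the sign with Table 3), and comfort non-inferiority if the lower limit is above -0.75.
- Choose the claim. For non-inferiority, reword Section 2.1 to say so. If no difference or a match is intended, require the whole interval to lie within ±0.10 and ±0.75, because one-sided non-inferiority does not establish it.
- Say whether the multiplicity adjustment applies to these two decisions, and keep the difference tests as descriptive.

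The cost is wording and those decisions; no new visits, measures or subjects are needed. Power with 60 completers and no true difference, without multiplicity adjustment (range over the two SDs):

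| | one-sided 0.05 | one-sided 0.025 |
|---|---|---|
| Acuity, either claim | over 99.9% | over 99.9% |
| Comfort, non-inferiority | 93% to 99.7% | 87% to 99% |
| Comfort, equivalence | 86% to 99.4% | 75% to 98.5% |

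Only comfort equivalence at one-sided 0.025 with the larger SD falls below the planned 80%.
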